6.7.1 Handling of study treatment and additional treatment

6.7.1.1 Handling of study treatment

Study drug must be received by a designated person at the study site, handled and stored safely and properly and kept in a secured location to which only the Investigator and designated site personnel have access. Upon receipt, all study drug must be stored according to the instructions specified on the labels and in the Investigator's Brochure. Clinical supplies are to be dispensed only in accordance with the protocol. Technical complaints are to be reported to the respective Novartis Country Organization (CO) Quality Assurance.

Medication labels will be in the local language and comply with the legal requirements of each country. They will include storage conditions for the study drug but no information about the subject except for the medication number.

The Investigator or designated site staff must maintain an accurate record of the shipment and dispensing of study drug in a drug accountability log. Monitoring of drug accountability will be performed by monitors during site visits or remotely and at the completion of the trial. Subjects will be asked to return all unused study drug and packaging at the end of the study or at the time of discontinuation of study drug.

At the conclusion of the study, and as appropriate during the course of the study, the investigator will return all unused study drug, packaging, drug labels, and a copy of the completed drug accountability log to the Novartis monitor or to the Novartis address provided in the investigator folder at each site.

6.7.1.2 Handling of additional treatment

Not applicable to this trial.

6.7.2 Instruction for prescribing and taking study treatment

The study drug (ofatumumab injections) will be administered starting at Visit 1. Drug will then be dispensed at scheduled visits throughout the treatment period. Starting at week 4, the subcutaneous injections should be administered at 4-week intervals (+/- 3 days).

Site personnel will provide training to subjects on the correct procedure for self-administration of s.c. injections. At Visit 1, subjects will receive the s.c. injection at site, where tolerability and vital signs will be assessed. Should the subject experience any tolerability event or post dose vital signs are not within reasonable limits, subject may remain at site until symptoms resolve or vital signs are within reasonable limits of baseline values.

In certain countries, e.g. Czech Republic, the local health authority requires subjects to remain at the site under observation for approximately 1 hour following first study drug dosing at Visit 1, where post vital signs will be collected. A longer observational period may be required if per investigator judgement these vital signs are not within reasonable limits of subject's baseline values. Subject or caregiver will inject the study medication under supervision of the study staff.

Following Visit 1, subjects may inject the study medication at home by themselves or have a caregiver who has been trained by the study staff on the proper technique and safety precautions, inject the study medication. Ability to self-administer injections must be demonstrated and documented before home-administration is permitted. Injection 2 (Day 7) will be overseen remotely by the designated site personnel to support the self/home administration and provide additional training as needed. Subjects will return to the site for the week 2 and 4 administrations. If a subject is unable/unwilling to self-administer injections, home-administration may be performed by another individual (e.g. partner, relative or a healthcare professional) who has accompanied the subject to the site and has been trained on and demonstrated ability to correctly administer the s.c. injections. In the exceptional circumstances, the subject may receive injections at the site, for example, subjects with severe neurological deficits should not self-administer injections.

Subjects should be instructed to record any missed doses in the subject diary provided for the study and to inform the study staff of any missed s.c. injection(s). This can be done at the visits and/or during the monthly remote contacts that are scheduled throughout the study during which, the study site staff will inquire about the subject's status and compliance with study treatment administration or issues related to the home administration.

Subjects who miss s.c. injections or temporarily interrupt study drug without discontinuing from the study or withdrawing consent, will be permitted to resume study drug if determined to

be safe and appropriate in the opinion of the investigator. When resuming study drug, the timing of the next s.c. injection will be determined based on the original study schedule as followed:

- If one monthly injection is missed by 1 week or less, the subject should take injection as soon as possible. The next injection should then be administered according to the original schedule.
- If one monthly injection is missed by more than 1 week, the subject should skip the dose and take the next dose at the time when the next injection would be due according to the original schedule.
- If two or more consecutive monthly injections are missed, the Investigator should inform the Sponsor before re-starting dosing.

Information about all kits of study medication assigned by the IRT will be recorded in the IRT system.

A subject will be provided with the injection instruction leaflet, which includes detailed information, precautions and instructions for administering s.c. injections using the AIs. This information should be reviewed with the subject (and his/her partner/relative as applicable) to ensure that they understand the correct procedure for self/home administration.

7 Informed consent procedures

The Investigator or his/her representative will explain the nature of the study, including the risks and benefits, to the subject or their legally authorized representative and answer all questions regarding the study.

Subjects must be informed that their participation is voluntary. Subjects or their legally authorized representatives will be required to sign a statement of informed consent that meets the requirements of 21 CFR 50, local regulations, ICH guidelines, privacy and data protection requirements, where applicable, and the IRB/IEC or study center.

Informed consent must be obtained before conducting any study-specific procedures (e.g. all of the procedures described in the protocol). The process of obtaining informed consent must be documented in the subject source documents.

The medical record must include a statement that written informed consent was obtained before the subject was enrolled in the study and the date the written consent was obtained. The authorized person obtaining the informed consent must also sign the ICF.

A copy of the ICF(s) must be provided to the subject or their legally authorized representative. Subjects who are rescreened are required to sign a new ICF.

The ICF will contain a separate section that addresses the use of remaining mandatory samples for optional additional research. The Investigator or authorized designee will explain to each subject the objectives of the additional research. Subjects will be told that they are free to refuse to participate and may withdraw their consent at any time and for any reason during the storage period. A separate signature will be required to document a subject's agreement to allow any remaining specimens to be used for additional research. Subjects who decline to participate in this optional additional research will document this.

Eligible subjects may only be included in the study after providing (witnessed, where required by law or regulation), Institutional Review Board (IRB)/Independent Ethics Committee (IEC)-approved informed consent.

If applicable, in cases where the subject's representative(s) gives consent (if allowed according to local requirements), the subject must be informed about the study to the extent possible given his/her understanding. If the subject is capable of doing so, he/she must indicate agreement by personally signing and dating the written informed consent document.

Information about common side effects already known about the investigational drug can be found in the Investigator's Brochure (IB). This information will be included in the subject informed consent and should be discussed with the subject during the study as needed, this includes changes in available standard of care if needed. Any new information regarding the safety profile of the investigational drug that is identified between IB updates will be communicated as appropriate, for example, via an investigator notification or an aggregate safety finding. New information might require an update to the informed consent and then must be discussed with the subject.

Women of child bearing potential must be informed that taking the study treatment may involve unknown risks to the fetus if pregnancy were to occur during the study and agree that in order to participate in the study they must adhere to the contraception requirements.

The following informed consents are included in this study:

- Main study consent, which also included:
 - A subsection that requires a separate signature for the 'Optional Consent for Additional Research using your Personal Data' to allow future research on data/samples collected during this study
 - Optional consent for activities that may be done outside of the study site
- As applicable, Pregnancy Follow-up consent for female subjects
- Optional informed consent for Home Nursing visits

A copy of the approved version of all consent forms must be provided to Novartis after IRB/IEC approval.

As per Section 4.6, during a public health emergency as declared by local or regional authorities i.e. pandemic, epidemic, or natural disaster, that may challenge the ability to obtain a standard written informed consent due to limits that prevent an on-site visit, the Investigator may conduct the informed consent discussion remotely (e.g. telephone, videoconference) if allowable by a local health authority. Guidance issued by local regulatory bodies, and ECs/IRBs on this aspect prevail and must be implemented and appropriately documented (e.g. the presence of an impartial witness, sign/dating separate ICFs by trial participant and person obtaining informed consent, etc.).

In case Home Nursing is implemented during a public health emergency as declared by local or regional authorities i.e. pandemic, epidemic, or natural disaster, or to reduce burden related to an on-site visits, a separate Home Nursing consent document must be used in addition to the main ICF.

8 Visit schedule and assessments

Assessment schedule (Table 8-1) lists all of the assessments and indicates with an "x" when they are performed. All data obtained from these assessments must be supported by the subject's source documentation.

Subjects should be seen for all visits/assessments as outlined in the assessment schedule (Table 8-1) or as close to the designated day/time as possible. Missed or rescheduled visits should not lead to automatic discontinuation. In case a visit is performed outside of the schedule, subsequent visits shall be performed in keeping with the original visit schedule. In addition to the scheduled visits, subjects may have unscheduled visits due to a MS relapse, an acute illness of undetermined cause, for other reasons, or at the discretion of the Investigator. Data collected during unscheduled visits will be recorded in the unscheduled visits CRF.

As per Section 4.6, during a public health emergency as declared by local or regional authorities i.e. pandemic, epidemic or natural disaster that limits or prevents on-site study visits, alternative methods of providing continuing care may be implemented by the investigator as the situation dictates. If allowable by local health authority, national and local regulations, and depending on operational capabilities, phone calls, virtual contacts (e.g. tele consultations) or visits by site staff/off-site healthcare professional(s) to the subject's home, can replace certain protocol assessments, for the duration of the disruption until it is safe for the subject to visit the site again. The subject may also opt to have some of the on-site visits performed by home nursing service at home as defined in the Table 8-1. If the Investigator delegates tasks to an off-site healthcare professional, the Investigator must ensure the individual(s) is/are qualified and appropriately trained to perform assigned duties. The Investigator must oversee their conduct and remain responsible for the evaluation of the data collected.

Subjects who prematurely discontinue the study for any reason should be scheduled for the EOS visit as soon as possible and then enter the Safety Follow-up period according to the schedule in Table 8-2. At this final visit, all dispensed investigational product should be reconciled, and the adverse events and concomitant medications recorded on the CRF.

 Table 8-1
 Assessment Schedule, Treatment

Period	Scre	ening	Treatment												
Visit Name	Screening	Baseline	Visit 12	Visit 2 (Remote contact Visit) ³	Visit 3 Week 2 ²⁴	Visit 4 Week 4	Visit 5 Week 8 ²⁴	Visit 6 Week 12 ²⁴	Visit 7 Week 24	Visit 8 Week 36 ²⁴	Visit 9 Week 48	Visit 10 Week 60 ²⁴	Visit 11 Week 72	Visit 12 Week 84 ²⁴	EOS/Visit 13 Week 96 ⁴
Visit Numbers ¹	1	20	100	110	120	130	140	150	160	170	180	190	200	210	220
Days	-60 to -8	-7 to 1 (Prior to 1 st dose/visit 1 start)	1	7 ±1	14 ±1	28 ±1	56 ±7	84 ±7	168 ±14	252 ±14	336 ±14	420 ±14	504 ±14	588 ±14	672 ±14
Informed Consents ²⁴	Х														
Demography, Height	Х														
Medical History	Х														
MS History/Treatments ⁵	Х														
Inclusion / Exclusion criteria	Х	Х													
Patient Training ^{6,7}		Х	Χ												
Drug dispensation			Х		Х	Х	Х	Х	Х	Х	Х	Х	Х	X ²⁸	
Site contact with subjects ⁸				Х					Мс	onthly bet	ween so	heduled	visits		
MS Relapse	X ²⁷	Х	Х	Х	Х	Х	Х	Х	Х	Х	Х	Х	Х	Х	Х
EDSS	Х	X ²⁰							Х		Х		Х		Х
MRI ⁹	X ¹⁰								Х		Х				X ¹¹
Office examinations 12			X ¹³						Х		Х		Х		Х
CCI															
LCVA			X ¹³								Х				Х
PROs ¹⁴			X 13			Х			Х		Х		Х		Х
CCI			X 13								Х				Х

Period	Scre	ening						Tre	eatment						
Visit Name	Screening	Baseline	Visit 12	Visit 2 (Remote contact Visit) ³	Visit 3 Week 2 ²⁴	Visit 4 Week 4	Visit 5 Week 8 ²⁴		Visit 7 Week 24	Visit 8 Week 36 ²⁴	Visit 9 Week 48	Visit 10 Week 60 ²⁴	Visit 11 Week 72	Visit 12 Week 84 ²⁴	EOS/Visit 13 Week 96 ⁴
Visit Numbers ¹	1	20	100	110	120	130	140	150	160	170	180	190	200	210	220
Days	-60 to -8	-7 to 1 (Prior to 1 st dose/visit 1 start)	1	7 ±1	14 ±1	28 ±1	56 ±7	84 ±7	168 ±14	252 ±14	336 ±14	420 ±14	504 ±14	588 ±14	672 ±14
CCI		X ²⁵	Х		Х	×	Х	X	×	х	Х	X	х	Х	×
CCI review ¹⁶		X ²⁵	Х		Х	Χ	Х	Χ	Х	Х	Χ	Χ	Х	Х	Х
Vital Signs	Х	X	X ¹⁷			X			Х		Χ		Х		Х
Physical Exam (including weight) ⁶	Х					Х			X		Х		Х		Х
Electrocardiogram (ECG)	Х														Х
Biomarker sampling ^{18,19}	Х					Х		Χ	Х	Х	Х	Х	Х	Х	Х
Total IgG, IgM levels	Х					Х			Х		Χ		Х		Х
Routine lab samples including urine	Х	X ²⁰				Х		Х	×		Х		Х		Х
Sample for CD19+ B-cells (all sites)		X				Х			X		Х		Х		Х
Sample for B-cell and T-cell subset testing (US sites only)		X				Х			×		Х		X		Х
Serological markers for hepatitis B and C ²⁶	Х														
Syphilis/Tuberculosis Assessment ²⁶	Х														
Pregnancy Test (serum) ²¹	Х										Х				Х

Period	Scre	ening						Tre	atment						
Visit Name	Screening	Baseline	Visit 1 ²	Visit 2 (Remote contact Visit) ³	Visit 3 Week 2 ²⁴	Visit 4 Week 4	Visit 5 Week 8 ²⁴	Visit 6 Week 12 ²⁴	Visit 7 Week 24	Visit 8 Week 36 ²⁴	Visit 9 Week 48	Visit 10 Week 60 ²⁴	Visit 11 Week 72	Visit 12 Week 84 ²⁴	EOS/Visit 13 Week 96 ⁴
Visit Numbers ¹	1	20	100	110	120	130	140	150	160	170	180	190	200	210	220
Days	-60 to -8	-7 to 1 (Prior to 1 st dose/visit 1 start)	1	7 ±1	14 ±1	28 ±1	56 ±7	84 ±7	168 ±14	252 ±14	336 ±14	420 ±14	504 ±14	588 ±14	672 ±14
Urine Pregnancy Test ²¹			X ¹³			Х	Х	Χ	Х	Х	X	Х	Х	Χ	Х
C-SSRS	Х		X ¹³		Х	Х	Х	Х	Х	Х	Х	Х	Х	Х	Х
Contraception Status ^{6,22}	Х	Х	Χ		Х	Х	Х	Χ	Х	Х	Х	Х	Х	Χ	Х
Concomitant medications ²³	Х	Х	Х	Х	Х	Х	Х	Х	Х	Х	Х	Х	Х	Х	Х
Adverse Events	Х	Х	Χ	Х	Х	Х	Х	Χ	Х	Х	Х	Х	Х	Х	Х
Subject Diary Review ⁶			Χ	Х	Χ	Χ	Χ	Χ	Х	Х	Χ	Х	Х	Χ	Х
Subject Disposition															Х

X Assessment to be recorded in the clinical database or received electronically from a vendor

¹ Visit structure given for internal programming purpose only

² Enrollment and first dose (usually expected on the same day). If first dose occurs on a different day after enrollment, the day of the first dose should be considered as Day 1

³ Remote contact visit to support home/self-administration of the study drug, support compliance with the diary and provide additional training as needed. An on-site visit is permitted in case the subject is unable/unwilling to self-administer injections.

⁴ EOS visit will be required for all subjects (subjects who permanently discontinue study drug and subjects who complete the study).

⁵ MS history including number of relapses in previous year and number of relapses in previous two years

⁶ Assessments captured as source data

⁷ At Baseline visit, patient training on CCI and and CCI (as required) CCI s's functionality and use. At day 1 patient training on study requirements including study drug administration using the autoinjector, ePRO, urine pregnancy tests used at home

⁸ Remote contact with subjects by site staff around the time of administration of ofatumumab self/home-injection. The contact should query about any new or worsening symptoms warranting an unscheduled visit, compliance with study treatment, injection reactions, results of home pregnancy testing and compliance with contraception requirements (when applicable). Method of contact can be via telephone, email or text message depending on the preference of each subject.

⁹ Restrictions may apply to MRI concerning steroid use, please refer to Section 8.3.4.

¹⁰ Screening MRI should be completed once all other screening eligibility assessments have been completed and confirmed to meet eligibility criteria

¹¹ MRI scan at the EOS visit is needed if there was no MRI scan in the previous 3 months.

Period	Scre	ening	Treatment												
Visit Name	Screening	Baseline	Visit 12	Visit 2 (Remote contact Visit) ³	Visit 3 Week 2 ²⁴	Visit 4 Week 4	Visit 5 Week 8 ²⁴		Visit 7 Week 24	Visit 8 Week 36 ²⁴	Visit 9 Week 48	Visit 10 Week 60 ²⁴	Visit 11 Week 72	Visit 12 Week 84 ²⁴	EOS/Visit 13 Week 96 ⁴
Visit Numbers ¹	1	20	100	110	120	130	140	150	160	170	180	190	200	210	220
Days	-60 to -8	-7 to 1 (Prior to 1 st dose/visit 1 start)	1	7 ±1	14 ±1	28 ±1	56 ±7	84 ±7	168 ±14	252 ±14	336 ±14	420 ±14	504 ±14	588 ±14	672 ±14

¹² Timed 25-Foot Walk, Nine Hole Peg Test

- via the CCI application will be conducted in countries where applicable languages are available. Data is collected continuously throughout the study. CCI should be dispensed at Baseline Visit, and given to the patient a minimum of 7 days prior to planned first study drug dose, and returned at EOS/Visit 13. On the days of the scheduled site visits, the CCI assessments will be performed under the supervision of trained site staff.
- ¹⁶ Subject to return CCI for data download and transfer. It's necessary to obtain CCI data at least 1 week before Visit 1. These data will be considered as CCI baseline data. Refer to Section 8.5.1.6 for more information.
- ¹⁷ Vital signs should be obtained 30-60 minutes before Day 1 s.c. injection (if premedication is administered, pre-injection vital signs should be obtained before premedication is administered), and again approximately 60 minutes post Day 1 s.c. injection
- ¹⁸ If the scheduled visit coincides with the day that study drug administration is scheduled, the subject should be instructed not to administer the injection before coming to the site so that the assessments can be completed prior to study drug administration.
- ¹⁹ Additional NfL and CCI sample to be collected in case of any unscheduled visit due to suspected MS relapse

CCI CCI, CCI

- ²⁰ Assessment must be completed to allow adequate time for results to be obtained before first study drug administration to ensure subject's eligibility
- Women of childbearing potential only Serum pregnancy tests will be conducted on an annual basis at site. Monthly urine pregnancy tests will be conducted between scheduled visits at home and on scheduled visits (in the absence of an annual serum pregnancy test) at site prior to the administration of study drug. The subject must contact the Investigator immediately in the case of a positive test for confirmatory testing at the Investigator's discretion.
- ²² Subject's contraception status must be reviewed and documented to ensure method of contraception continues to be appropriate per protocol requirement for highly effective contraception.
- ²³ Including corticosteroids used to treat MS relapse; any new started MS treatment as applicable (for subjects who have discontinued study medications).
- ²⁴ Visit can be performed at the site or at subject's home with support of home nursing service. In this case an additional home nursing ICF must be signed.
- ²⁵ CCI and CCI should be given to the patient minimum 7 days prior to planned first study drug dose.
- To be assessed locally. If local testing is not feasible at a site, then these tests may be done by the Central Laboratory to assess patient's eligibility.
- ²⁷ MS relapses occurring after ICF signature should be assessed according to Section 8.3.1 and recorded on the Summary of MS Relapses eCRF.
- ²⁸ One additional medication kit can be dispensed at Visit 12/week 84, and taken by the subject prior to or no later than the day of the EOS visit, to ensure the subject does not have an interruption in treatment between study completion and start of commercial ofatumumab via prescription or via PTA mechanisms.

¹³ To be completed prior to first study drug administration

¹⁴ Patient Reported Outcomes: CCI

Table 8-2 Assessment Schedule, Safety Follow-up

Period		Po	st-Treatment Follow-up				
Visit Name	Safety Follow-up Visit 1	Safety Follow-up Visit 2	Additional Follow-up Visits ¹	End of Safety Follow-up Visit			
Days	EOS + 3 Months ±14	EOS + 6 Months ±14	Every 3 months ±14 after Safety Follow-up Visit 2	Early discontinuation	Completion ⁶		
MS Relapse	X	Х	X	Х			
EDSS	Х	Х	X	Х			
Physical Exam (including weight)	Χ	Х	X	X			
Vital Signs	Х	X	X	X			
Routine lab samples including urine	X	X	X	×			
Sample for CD19+ B-cells (all sites)	Х	Х	х	х			
Sample for B-cell and T-cell subset testing (US sites only)	X	Х	Х	х			
Total IgG, IgM levels	Х	Х	X	Х			
Neurofilament and CCI Sampling	X	Х	Х	х			
Urine Pregnancy Test ²	X	Х		X ⁷			
Contraception Status ^{3,4}	Х	Х		X ⁷			
Concomitant medications ⁵	Х	Х	X	Х	Х		
Adverse Events	Х	Х	X	X	Х		
Safety Follow-up Subject Disposition				X	Х		

X Assessment to be recorded in the clinical database or received electronically from a vendor

¹ As needed for the subjects requiring prolonged Immunoglobulin (IgG and IgM) monitoring; refer to Section 9.2.1.

² Pregnancy test is conducted on female subjects only. Urine pregnancy tests will be conducted at all scheduled visits as indicated in Table 8-2. Monthly urine pregnancy tests will be conducted at home between site visits. The subject must contact the Investigator immediately in the case of a positive test for confirmatory testing at the Investigator's discretion.

³ Subject's contraception status must be reviewed and documented to ensure method of contraception continues to be appropriate per protocol requirement for highly effective contraception.

⁴ Assessments captured as source data

5 Including corticosteroids used to treat MS relapse; any newly started MS treatment as applicable.

6 For subjects completing Safety Follow-up, the End of Safety Follow-up visit will be performed by telephone contact (after the central laboratory results have confirmed that IgG and IgM results are ≥ screening or LLN) to inform the subject that his or her participation in the Safety Follow-up has ended; the disposition form will be completed at that time and the AE and concomitant medications eCRFs will be updated if necessary to record any new or worsening events or medication changes since the last clinic visit. Please refer to Section 9.2.1.

7 To be performed only if less than 6 months after stopping study medication

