8.4.5 Laboratory evaluations

A central laboratory will be used for analysis of all specimens collected. Details on the collections, shipment of samples and reporting of results by the central laboratory are provided to Investigators in the laboratory manual. Abnormal laboratory parameters, inconsistent with the clinical presentation of MS or which cause suspicion of an underlying medical condition, should be repeated for confirmation.

All abnormal lab results must be evaluated for criteria defining an adverse event and reported as such if the criteria are met. For those lab adverse events, repeated evaluations are mandatory

until normalization of the result(s) or until the result is no longer considered clinically significant.

As per Section 4.6, during a Public Health Emergency, as declared by Local or Regional authorities i.e. pandemic, epidemic or natural disaster, limiting or preventing on-site study visits, alternative methods of providing continuing care may be implemented. Standard safety laboratory testing may be conducted by a local laboratory if it is possible to arrange for the laboratory panels (i.e. scheduled chemistry, hematology and urinalysis) to be performed if subject cannot attend scheduled on-site clinic visit or other issues exist that would either prohibit the collection or shipment of laboratory samples to the central laboratory in accordance with the laboratory manual for the study. A local laboratory may also be used to obtain CD19+ B-cell, IgG and IgM counts at the investigator's discretion. The investigator must assure to collect and file all local laboratory reports, certifications and reference ranges in the subject medical record or chart. Data obtained from local laboratories will be used for the investigator's purposes only (to continue monitoring and following-up on subject safety issues) and will not be included in the study clinical database or study analyses.

Scheduled or unscheduled subject study visits can be performed once feasible and considered safe for subjects to attend the clinical appointments.

Table 8-4 Laboratory Assessments

Test Category	Test Name
Hematology	Blood samples will be collected according to the schedule in Table 8-1 and Table 8-2. Hematocrit, Hemoglobin, Platelets, Red blood cell (RBC) count, Total white blood cell (WBC) count and WBC differential counts (Basophils, Eosinophils, Lymphocytes, Monocytes, Neutrophils).

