8.4.6 Pregnancy and assessments of fertility

Serum pregnancy tests will be conducted for all women of childbearing potential at Screening, annually and EOS visits. Urine pregnancy tests will be conducted for all women who are of child bearing potential at all other planned clinic visits as indicated in Table 8-1 and Table 8-2 prior to study drug administration. In addition, the subjects will be provided with urinary pregnancy test kits for monthly home pregnancy testing required between the scheduled clinic visits prior to study drug administration. The subjects will document the date and result of each home pregnancy test. In case of a positive test result, the subject must contact the Investigator immediately for confirmatory testing at the Investigator's discretion.

In addition, the Investigator will review the contraception status with the subject at each visit to ascertain that the subject continues to comply with protocol requirements for highly effective contraception as applicable.

All pre-menopausal women who are not surgically sterile will have pregnancy testing. A woman is considered of childbearing potential from menarche and until becoming post-menopausal unless permanently sterile. Permanent sterilization methods include hysterectomy, bilateral salpingectomy and bilateral oophorectomy. Medical documentation of oophorectomy, hysterectomy, or tubal ligation must be retained as source documents.

A postmenopausal state is defined as no menses for 12 months without an alternative medical cause and an appropriate clinical profile.

In absence of a medical documentation confirming permanent sterilization, or if the post-menopausal status is not clear, the investigator should use his medical judgment to appropriately evaluate the fertility state of the woman and document it in the source document. Additional pregnancy testing might be performed if required by local requirements.

As per Section 4.6, during a public health emergency as declared by local or regional authorities' i.e. pandemic, epidemic or natural disaster, that limits or prevents on-site study visits, if subjects cannot visit the site to have serum pregnancy tests, urine pregnancy test kits may be used. Relevant subjects can perform the urine pregnancy test at home and report the result to the site.

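### Table 8-1 marks both a urine and a serum pregnancy test at Week 48 and EOS, while footnote 21 and Section 8.4.6 call for the site urine test only where no serum test is due

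*Protocol*

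**What the plan says.** Three places in the protocol govern pregnancy testing during treatment.

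- **Table 8-1, grid.** The row "Pregnancy Test (serum") is marked at Screening, Week 48 and EOS/Week 96. The row "Urine Pregnancy Test" is marked at Visit 1 and at every visit from Week 4 to EOS. Both tests are therefore marked at Week 48 and EOS.
- **Table 8-1, footnote 21**, attached to both rows. "Serum pregnancy tests will be conducted on an annual basis at site". Site urine tests are done "on scheduled visits (in the absence of an annual serum pregnancy test) at site prior to the administration of study drug".
- **Section 8.4.6.** "Serum pregnancy tests will be conducted for all women of childbearing potential at Screening, annually and EOS visits". Urine tests are done "at all other planned clinic visits as indicated in Table 8-1 and Table 8-2 prior to study drug administration". Home urine kits cover the months between clinic visits.

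Two further provisions bear on timing. Section 8.4.5 says: "A central laboratory will be used for analysis of all specimens collected". Footnote 18, attached to the biomarker row, says that if a visit falls on a dosing day "the subject should be instructed not to administer the injection before coming to the site".

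**The concern.** The grid asks for two tests at Week 48 and EOS, whereas the footnote and Section 8.4.6 ask for one. Section 8.4.6 also refers back to the table for the urine visits, so it points to a grid that does not match it.

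The difference matters because the two tests are not handled alike. The words placing the test before dosing are attached to the urine test in both footnote 21 and Section 8.4.6. Nothing comparable is attached to the serum test, and no passage holds the Week 48 dose until the serum result is known. Section 9.1.1 lists pregnancy as a reason for mandatory discontinuation of study drug. What is at stake is whether sites apply the same check before a scheduled dose in women of childbearing potential.

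**Working it through.** The plan states no figure to reproduce. The check sets the schedule entries side by side and then bounds the size.

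**1. Overlap of the two rows.** Read across the 15 visit columns of Table 8-1:

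| Test | Marked at |
|---|---|
| Serum | Screening, Week 48, EOS |
| Urine | Visit 1, Weeks 4, 8, 12, 24, 36, 48, 60, 72, 84, EOS |

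The overlap is exactly Week 48 and EOS.

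**2. Are these dosing weeks?** Section 6.7.2 gives injections every 4 weeks from Week 4, within 3 days either way. Week 48 is Day 336, and 336 / 28 = 12. Week 96 is Day 672, and 672 / 28 = 24. Both lie on the 4-week grid. Drug is dispensed at Week 48. At EOS a dose arises only if the optional kit of footnote 28, dispensed at Week 84, is taken on the day of that visit.

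**3. Last earlier pregnancy result if the site urine test is omitted.** The 4-weekly points between the Week 36 and Week 48 visits are Weeks 40 and 44. The last home urine test before the Week 48 dose is therefore at about Week 44. The points between Weeks 84 and 96 are Weeks 88 and 92, so for a dose on the EOS day it is at about Week 92.

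**4. Can the serum result be relied on before the dose?** Section 8.4.5 sends specimens to the central laboratory. The hepatitis and syphilis/tuberculosis rows carry footnote 26, which provides for local testing; the serum pregnancy row does not. No turnaround is given in the protocol. A same-day result is neither promised nor ruled out.

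**5. Size.** Inputs:

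- planned sample size 555 (Section 5);
- share who are women of childbearing potential: not in the documents, assumed 60% to 70%, so 555 x 0.60 = 333 and 555 x 0.70 = 388.5, taken as 389;
- contraceptive failure rate below 1%: exclusion criterion 6 gives the figure without a time unit, assumed to be per year;
- interval since the last home test: 28 days.

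Expected pregnancies arising in that interval = women x annual rate x 28/365:

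- 333 x 0.01 x 28/365 = 0.26
- 389 x 0.01 x 28/365 = 0.30
- all 555, as an extreme: 555 x 0.01 x 28/365 = 0.43

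For the assumed share and rate these are upper figures. They suppose that nobody has left treatment, that every site omits the urine test, that every dose falls on the visit day, and that no serum result is back in time. If every woman also took the additional kit on the EOS day, the 0.30 would double to about 0.60.

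**The case against.** The strongest reply is that the grid and its footnote do not conflict. The urine row carries footnote 21, so each mark in it is subject to that footnote, and the marks at Week 48 and EOS serve as a fallback when serum is not drawn. Section 8.4.6 foresees such a case in a public health emergency. This reading is tenable, but it does not close the gap: under it only serum is done at Week 48, and nothing ties the serum result to the dose.

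Several other points stand and limit the concern.

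- Neither footnote 21 nor Section 8.4.6 mentions a central laboratory; footnote 21 says serum tests are conducted at site. The central-laboratory premise comes from the general sentence in Section 8.4.5, which has local exceptions, and result reporting is left to a laboratory manual.
- Footnote 18 is conditional. After the first weeks most doses are taken at home, and the Week 48 visit window is 14 days either way, so visit and dose need not coincide. When they do not, a home urine test may cover the dose.
- The last paragraph of Section 8.4.6 tells subjects to test urine first and dose only on a negative result. It follows directly on the public-health-emergency text, so whether it reaches an ordinary Week 48 visit is arguable.
- Contraception is required for 6 months after stopping, so a woman who conceives between Weeks 44 and 48 is already within the precaution period from earlier doses. The serum test drawn at the visit would be expected to detect the pregnancy later and lead to discontinuation.

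A reader might infer that the protocol has sites dose at Week 48 with no pregnancy result at all. The documents do not support that: a home result from about Week 44 should exist, the grid still marks the urine test, and no turnaround is stated from which a late serum result could be concluded.

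**Conclusion.** The inconsistency is real and confined to two visits. Table 8-1 and the text give different testing instructions at Week 48 and EOS, and sites can defensibly follow either. Where the urine test is omitted and the dose falls on the visit day, it may be given with no pregnancy result newer than about four weeks. That outcome is conditional on the timing of the dose and of the serum result; the documents do not make it certain or routine.

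The expected count is very small, about 0.26 to 0.30 pregnancies at the Week 48 dose as an upper figure. It rests on the assumed share of women and on reading the failure rate as annual. It could concern up to every woman of childbearing potential still on treatment once, and a second time only with the additional kit taken on the EOS day. No endpoint, estimate or analysis is affected. The point merits correction because it concerns a safety check and costs little, not because of its numerical size.

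**What to change.** Reconcile the urine and serum rows of Table 8-1, footnote 21 and Section 8.4.6 into a single instruction for Week 48 and EOS. Make that instruction consistent with the protocol's own wording that pregnancy testing precedes dosing, including the EOS-day dose that footnote 28 allows. This review does not say which test or rule should apply; that is for the sponsor and its clinical and safety functions.

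The cost is wording in one table, one footnote and one section, taken through the amendment procedure of Section 14.1. No data collection or analysis has to change. The current SAP amendment is dated April 2025 and marked as prior to database lock, so few treatment visits may remain. The documents do not say how many.
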